A randomized controlled trial comparing free-hand versus distal targeting jig-based for distal interlock screw placement

Version 6 10/25/2023

NCT05613257

[name], FAAOS

[name], FAAOS

Cedars Sinai Medical Center

TABLE OF CONTENTS

PROTOCOL SUMMARY	3
GENERAL INFORMATION	3
1.0 BACKGROUND, RATIONALE.....	3
2.0 STUDY OBJECTIVES.....	4
3.0 STUDY POPULATION	4
3.1 SELECTION OF THE STUDY POPULATION	4
3.2 INCLUSION CRITERIA.....	4
3.3 EXCLUSION CRITERIA.....	4
3.4 SUBJECT SCREENING AND ENROLLMENT	4
3.5 SUBJECT RECRUITMENT	5
4.0 STUDY DESIGN AND METHODS.....	5
5.0 DATA COLLECTION AND MANAGEMENT	5
5.1 DATA PROCUREMENT	5
5.2 TIME PERIOD OF DATA UNDER REVIEW	5
5.3 VARIABLES COLLECTED	5
5.4 SOURCE DOCUMENTS.....	6
5.5 DATA COLLECTION AND STORAGE.....	6
5.6 CONFIDENTIALITY AND SECURITY OF DATA.....	6
6.0 DATA AND SAFETY MONITORING	6
6.1 DATA AND SAFETY MONITORING PLAN.....	6
6.2 QUALITY CONTROL AND QUALITY ASSURANCE.....	6
7.0 STATISTICAL CONSIDERATIONS.....	7
7.1 STUDY OUTCOME MEASURES.....	7
7.2 SAMPLE SIZE CONSIDERATIONS.....	7
8.0 REFERENCES	7

PROTOCOL SUMMARY

Purpose and Knowledge to be Gained	
 The purpose the research is to compare a modern proximally-based distal targeting device and free-hand techniques for placement of interlocking screws in lower extremity nailing
Research Procedures	
 The primary research procedures are using jig-based distal targeter for lower extremity nailing orthopedic surgery procedures
Subject Population	
 18 years old and above Undergoing intramedullary fixation of femur or tibia shaft for acute fracture or nonunion
Duration	
 The study includes 1 visit. The total study duration is 1 year

GENERAL INFORMATION

CSMC Co-Investigators	[name], FAAOS [name], FAAOS [name], FAAOS [name], MHDS [name], Study Coordinator
Sponsor/Funder	Stryker [name]
Collaborating Institutions Involved in the Research	N/A

1.0 BACKGROUND, RATIONALE

Background: Interlocking screw placement in intramedullary nailing of femoral and tibial shaft fractures improves rotational and length stability. However, free-hand perfect circle techniques can be technically challenging and may take up to an hour with increased radiation exposure to the surgeon and patient (Whatling et al, Injury 2006). Newer technologies aimed at reducing fluoroscope use such as electromagnetically-based aiming devices may increase operative time (Maqungo et al, JOT 2014). Proximally-based jigs have been shown to reduce fluoroscopy time in cadavers (Miclau et al, Arch Orthop Tr Surg 1998), however have not been studied clinically.

We propose a prospective, randomized controlled trial comparing a modern proximally-based distal targeting device and free-hand techniques for placement of interlocking screws in lower extremity nailing.

2.0 STUDY OBJECTIVES

Outcomes:

- Primary outcomes: radiation exposure, time, accuracy of placement (right angle to rod).
 - Each distal interlock will be considered a separate outcome
 - The first fluoroscopy shot to localize the jig or obtain a perfect circle is considered start time. The surgeon will note the hour, minute, and seconds of the time based on the wall clock in the operating room.
 - The last shot to confirm complete seating of the screw will be considered end time. The surgeon will note the hour, minute, and seconds of the time based on the wall clock in the operating room.
- Secondary outcomes:
 - accuracy of placement (right angle to intramedullary nail).
 - Number of complete misses of the nail with the drill or the screw
 - comparison of learning curve between distal targeter and freehand techniques stratified by level of training
 - The level of training of the surgeon
 - Experience level of the surgeon
 - estimated number total number of intramedullary nails placed
 - time since the last intramedullary nail placement
 - estimated number of nails placed per month over the last year
 - number of times the surgeon has used the distal targeting system
 - Comparison of tibia vs femur antegrade nails

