7.0 STATISTICAL CONSIDERATIONS

7.1 STUDY OUTCOME MEASURES

- Primary Outcome analysis: 2 tailed T-test for average length of surgery (skin to skin), average time to place 2 interlocks (start time when nail is seated and surgeon states s/he is ready to proceed with distal interlocking screw placement). Average radiation used in microGrays. Femur vs tibia average time to place 2 interlocks and average radiation exposure.
 - To compare time and accuracy of placement only data from surgeons who have performed both DT and FH techniques more than 5 times will be included.
- Secondary outcomes: t-test accuracy of screw placement (perpendicular to nail)
 - Multivariate regression evaluating predictors of time to placement
 - Level of training
 - Number of cases performed
 - Number of interlocking screws placed
 - Time since last case
 - Learning curve assessment
 - Time of each interlocking screw placement will be correlated with number of interlocking screws placed
 - Time of procedure and accuracy of placement will be analyzed in increments of 5 cases to evaluate for number of cases required to reach plateau
 - Data will be stratified by level of training

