7.2 SAMPLE SIZE CONSIDERATIONS

- Power: Based on a more recent paper from Konda et al, the average time for distal interlocking screw placement was 616 seconds in the control and 344 seconds in the distal targeting with an SD of 192 seconds. This suggests that a total of 30 patients would need to be enrolled for each cohort to detect a 44% decrease in the amount of time required for distal interlocking screw placement with the distal targeter with 90% power at 5% significance. (sealedenvelope.com power calculator on-line)
 - Estimating a 75% participation rate, we intend to enroll 60 patients (30 in each cohort – tibia and femur surgeries) that meet the sub-study criteria
 - Given that 9% of the currently enrolled patients (included in the main study) will not meet the sub-study criteria (retrograde nails instead of antegrade), we intend to enroll a total of 66 total patients for this study (includes patients for main study and sub study).

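### The accuracy t-test appears to count each distal screw as an independent observation; if screws within a nail are positively correlated, its type I error exceeds 5%

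*Combined protocol and SAP*

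**What the plan says.** Section 2.0 opens its outcome list with "Primary outcomes: radiation exposure, time, accuracy of placement (right angle to rod", and the first line beneath it reads "Each distal interlock will be considered a separate outcome". This is the only statement of unit in the documents that covers accuracy. The same section lists accuracy again among the secondary outcomes.

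Section 7.1 places the accuracy analysis under the secondary heading: "Secondary outcomes: t-test accuracy of screw placement (perpendicular to nail". It gives no unit for that test, no averaging over the screws of a nail, and no mixed model, GEE or cluster-robust standard error. It also restricts the time and accuracy comparisons to surgeons with more than five uses of each technique.

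For time, section 7.1 is explicit. The comparison is of "average time to place 2 interlocks", which yields one figure per nail.

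Section 4.0 sets the technique by calendar period for every patient operated on in that period. No screw is allocated on its own.

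**The concern.** Two screws in one nail share the patient, the nail and the assigned technique. Their angles are measured against the same nail, so their errors may well go together. An ordinary two-sample t-test takes every observation as independent. If it is fed screws, it treats a nail with two screws as two pieces of evidence, and with positive correlation the standard error is too small.

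At stake is the between-technique accuracy result. A difference in screw angle could be declared significant more often than the nominal 5%, with an interval that is too narrow.

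**Working it through.** **The plan's own figure.** The documents give no sample size, SD or effect for accuracy. The only calculation, in section 7.2, is for time: "616 seconds in the control and 344 seconds in the distal targeting with an SD of 192 seconds", "with 90% power at 5% significance". The difference is 616 − 344 = 272 s. Per technique arm, 2 × (1.960 + 1.282)² × 192² / 272² = 10.5, so 11; two arms make 22; 22 / 0.75 = 29.3, so 30. Two such cohorts make 60, and 60 / 0.91 = 65.9, so 66. The stated numbers therefore reproduce if a cohort means tibia or femur and the 75% participation rate is already included. They rest on time and say nothing about accuracy.

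**Inputs for accuracy.**
- Screws per nail: 2, taken from the time outcome in 7.1; the number is not stated for accuracy.
- Nominal level: two-sided 5%. The two-sided form is stated for the primary analysis in 7.1 and the 5% for the time calculation in 7.2.
- Within-nail correlation r: not in the documents. Assumed range 0 to 0.7.

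**Formula.** Let each screw have variance σ², with k nails per arm and two screws per nail. The mean of the 2k screws has true variance σ²(1 + r)/(2k). The screw-level t-test uses about σ²/(2k). The variance is thus understated by the factor 1 + r, the correct interval is √(1 + r) times wider, and the true type I error is 2 × [1 − Φ(1.96/√(1 + r))].

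For example, at r = 0.5: 1.96/√1.5 = 1.600, and 2 × [1 − Φ(1.600)] = 0.110.

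**Results.** The simulations used independent nails, normally distributed values and 40,000 runs per setting.

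| r | √(1 + r) | Screw-level test, formula | Screw-level, simulated, 30 nails per arm | Screw-level, simulated, 15 nails per arm | Nail-mean test, simulated, 30 / 15 nails per arm |
|---|---|---|---|---|---|
| 0 | 1.00 | 5.0% | 5.0% | 4.9% | 5.1% / 4.9% |
| 0.1 | 1.05 | 6.2% | 6.2% | 6.1% | 5.0% / 5.0% |
| 0.3 | 1.14 | 8.6% | 8.5% | 8.8% | 4.8% / 5.1% |
| 0.5 | 1.22 | 11.0% | 11.1% | 11.2% | 5.1% / 5.0% |
| 0.7 | 1.30 | 13.3% | 13.3% | 13.8% | 5.1% / 5.1% |

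The inflation hardly depends on the number of nails. This matters because the experience restriction in 7.1 leaves the size of the accuracy sample unknown. At r = 0.5, 60 screws per arm carry the information of 60/1.5 = 40, and a reported p of 0.04 corresponds to about 0.09.

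**Alternative reading.** If the first and second screws are each tested on their own, every test has one value per nail and within-nail correlation does not distort it. There are then two tests of one question. If they were independent, the chance of at least one false positive would be 1 − 0.95² = 9.75%; with positive correlation it is lower.

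**The case against.** The strongest reply is that pooling is inferred. A reader might conclude that the plan states outright that screws are pooled as independent observations. It does not. The sentence in 2.0 is followed by rules for noting start and end times, so it could be a recording rule, or it could mean that each screw position is analysed separately. Where 7.1 does give a unit for a between-technique comparison, it is the nail or the operation, as in "average time to place 2 interlocks" and "2 tailed T-test for average length of surgery (skin to skin". That practice weakens the inference for accuracy. It does not remove it: the time outcome is explicitly aggregated within the nail, accuracy is not, and nothing replaces the unit statement in 2.0.

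A reader might also take the correlation as established, on the ground that both screws share one film, one operator and one jig alignment. The documents say only that measurements come from radiographs, and none of these three is stated. A positive r is likely but assumed, and a low value gives only a small inflation.

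Finally, it would be tempting to extend the point to the main time result or to the sample size. Neither follows: the time test is per nail, and section 7.2 rests on time. The learning-curve analysis in 7.1 does use the time of each screw, but it is not a comparison of techniques and lies outside this point.

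**Conclusion.** The concern holds for the between-technique accuracy test. On the most natural reading of 2.0 with 7.1, that test has the screw as its unit and no allowance for the nail. Its true type I error is then about 6% to 13% for r from 0.1 to 0.7, and 5% only if r is zero. These figures assume two screws in every nail and independent nails. On the alternative reading the problem is multiplicity, up to 9.75%. On the recording-rule reading the plan simply leaves the unit of the test open. One stated unit resolves all three.

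The weight is moderate. Accuracy appears as both primary and secondary in 2.0 and is analysed as secondary in 7.1. A misleading p-value matters under either label, but the main time comparison is unaffected.

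The table's values near 5% for nail means should not be read as showing that a per-nail test is fully valid in this trial. They assume independent nails. Technique is assigned by calendar period and surgeons treat several patients, and averaging within a nail removes neither form of clustering. Those are separate issues.

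**What to change.** In sections 2.0 and 7.1, state that the patient (nail) is the unit of the between-technique accuracy test. Then choose one of two analyses before any data are compared:

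- One accuracy value per nail, for example the mean over its distal interlocks of the absolute deviation from 90 degrees, compared by t-test. The absolute value keeps errors on either side of 90 from cancelling. It also fixes how accuracy is scored, which is a separate choice from the unit and should be stated as such.
- Screw-level values in a model with technique as a fixed effect and a random effect for patient. This copes better with unequal numbers of screws per nail and with a patient who contributes two nails.

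If the sentence in 2.0 is meant only as a rule for recording each screw, say so there.

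The cost is a change of wording and no new data. With two screws in every nail and the same score, the estimated difference between techniques does not move. The downside is an interval wider by about √(1 + r): 5% at r = 0.1, 22% at 0.5 and 30% at 0.7.

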4.0 STUDY DESIGN AND METHODS

This study will be a prospective, randomized control trial. Patients will be randomized to perform distal interlock screen insertion either by freehand or distal targeting for all lower extremity nails.

1. All patients undergoing femoral or tibial nailing will undergo one method of interlock placement starting on the first of the month starting with free-hand locking. The method of interlocking screw placement will then switch to jig-based screw placement at the first of the following month. The method of screw placement will alternate each week until enrollment is complete. This method of enrollment for clinical modalities that are already in common use has previously been described with the PREP-IT trials. [Slobogean et al, JAMA Netw Open 2020]
2. Due to the nature of the distal targeting jig's construction, there may be instances where its use is not possible due to interference with other surgical instrumentation, and an intraoperative decision must be made to place screws with the freehand technique. Patients randomized to the jig-based placement arm but are ultimately treated with freehand placement will be documented and reported as crossover patients (per the CONSORT framework).
3. Patients randomized to their respective groups will ultimately undergo intention-to-treat analysis.

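### The clock rules for the powered time outcome can leave jig mounting untimed while freehand perfect-circle work is timed

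*Combined protocol and SAP*

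**What the plan says.** Section 2.0 (Study Objectives) lists time as a primary outcome and starts the clock as follows: "The first fluoroscopy shot to localize the jig or obtain a perfect circle is considered start time". It ends it so: "The last shot to confirm complete seating of the screw will be considered end time". Each distal interlock is treated as a separate outcome, and the surgeon notes both times from the wall clock.

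Section 7.1 (Study Outcome Measures) gives a different start for the time to place two interlocks: "start time when nail is seated and surgeon states s/he is ready to proceed with distal interlocking screw placement". The primary analysis there is a "2 tailed T-test for average length of surgery (skin to skin), average time to place 2 interlocks", plus radiation.

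Section 4.0 foresees that the jig will sometimes fail to fit: "there may be instances where its use is not possible due to interference with other surgical instrumentation". Those patients are placed freehand, reported as crossovers and analysed by intention to treat.

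Section 7.2 powers the trial on placement time, "to detect a 44% decrease in the amount of time required for distal interlocking screw placement with the distal targeter", from planning values of "616 seconds in the control and 344 seconds in the distal targeting with an SD of 192 seconds".

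No section asks for jig assembly or mounting to be timed. The variable list in 5.3 includes length of surgery but no set-up time (nor does it list the interlock times themselves).

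**The concern.** A fair time comparison starts both arms at the same point in the operation. The section 2.0 rule instead starts each arm at an event belonging to its own technique. For freehand, that event opens the preparatory imaging. For the jig, it comes after the preparatory step of attaching the device. The operator who notes the time knows which technique is in use.

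Section 7.1 does not settle the matter. Readiness to proceed may be declared before or after the jig is mounted, and the text does not say which.

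The jig's overhead is part of the question this trial asks. Section 1.0 notes that another newer aiming technology may lengthen operations. Section 4.0 expects some jig attempts to be abandoned; under the 2.0 rule, time spent on such an attempt is uncounted if no localizing shot was taken. The trial could then report a saving that partly reflects where the clock starts. A larger sample would not cure that, because it is bias and not noise.

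**Working it through.** **1. What each rule puts on the clock**

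| Step | Section 2.0 rule | Section 7.1 rule |
|---|---|---|
| Jig assembly and mounting | Before the start, since the jig must be in place to be localized | Not stated |
| Imaging to localize the jig | Timed | Timed if after readiness is declared |
| Freehand preparation before the first shot (e.g. positioning the fluoroscope) | Untimed | Timed if after readiness is declared |
| Freehand perfect-circle imaging | Timed from its first shot | Timed if after readiness is declared |
| Jig attempt abandoned before any localizing shot | Untimed | Not stated |

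The 2.0 rule treats the arms differently by construction. The 7.1 rule is the same sentence for both arms and is only ambiguous.

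**2. The plan's own figure**

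Inputs (7.2): means 616 and 344 s, SD 192 s, 90% power, 5% significance; two-sided (7.1).

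- Difference: 616 − 344 = 272 s; 272/616 = 44.2%, the stated 44%.
- n per arm = 2 × (1.960 + 1.282)² × 192²/272² = 10.5, so 11 per arm and 22 in total.
- Allowing for 75% participation: 22/0.75 = 29.3, so 30. This matches 30 per cohort if a cohort is one bone holding both arms, about 15 per arm.
- 60/0.91 = 65.9, so 66, as stated.

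No planning figure is disputed here.

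**3. Effect of untimed set-up**

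Let m be untimed jig set-up and f untimed freehand preparation, both in seconds. Then

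measured saving = all-in saving + (m − f).

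Each net untimed second adds one second to the jig's apparent advantage. The documents give neither m nor f.

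**4. Illustration**

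Assumptions: f = 0; m = 60 or 120 s, chosen only for illustration; SD stays at 192 s; the 344 s planning mean excludes set-up. Normal approximation:

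power = Φ(Δ/(192 × √(2/n)) − 1.96).

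With 15 per arm, 192 × √(2/15) = 70.1 s. With 30 per arm (both bones pooled), 192 × √(2/30) = 49.6 s.

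| m (s) | Share of 272 s | All-in saving (s) | n per arm, 90% power | Power for all-in saving, 15 per arm | Chance of a significant result for the jig if the all-in saving is zero, 15 / 30 per arm |
|---|---|---|---|---|---|
| 0 | 0% | 272 | 11 | 97% | 2.5% / 2.5% |
| 60 | 60/272 = 22% | 212 | 18 | 86% | 13% / 23% |
| 120 | 120/272 = 44% | 152 | 34 | 58% | 40% / 68% |

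Example, m = 60: 212/70.1 − 1.96 = 1.06, giving 86%; and 60/70.1 − 1.96 = −1.10, giving 13%. The last column rises with sample size, as expected of a bias.

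**The case against.** The strongest reply is that the primary analysis already contains a neutral measure. Skin-to-skin time starts and stops identically in both arms and includes any mounting, successful or abandoned, between incision and closure. If the jig only moved work ahead of the interlock clock, no matching skin-to-skin saving would appear. This stands as partial mitigation. However, skin-to-skin time carries the variation of the whole operation, has no power calculation, and does not correct the placement-time result on which the trial is sized.

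Second, the 7.1 start can be read naturally as including mounting, since mounting is part of proceeding to distal locking. That reading is open, so a reader who infers that both rules share the same flaw goes further than the text. Only the 2.0 rule separates the arms.

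Third, a reader might infer that all the bias runs one way. The documents do not support that: under 2.0, freehand preparation before the first shot is untimed too, and only the net matters.

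Fourth, no section says when the jig is assembled or mounted. Because 2.0 counts each interlock separately, one mounting need not affect every timed screw. This limits how firmly the size can be stated, but it does not make the start event neutral.

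Finally, placement-only time is a legitimate target. It is, provided it is labelled as such and the set-up it leaves out is reported beside it.

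**Conclusion.** The concern holds in a limited form. If the section 2.0 rule is followed, the powered time comparison leaves out jig mounting while timing freehand's perfect-circle work, which tilts it toward the jig. If the 7.1 rule is followed, the same omission is possible but not built in. The step from localizing the jig to a jig already in place is an inference from the wording, though a short one.

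The size cannot be established from the documents. The 22% to 44% range rests on assumed mounting times of 60 to 120 s with no offsetting freehand preparation. The power figures also assume that the 344 s planning mean excludes set-up, and 7.2 does not say which clock produced 616 and 344 s. One could go on to suppose that set-up might account for the whole planned saving. That would need about 272 s of net untimed work, which merely restates the planned effect, and nothing in the documents points to such a duration.

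This should be corrected: time is a primary outcome and the one the trial is powered on, and mounting time not recorded in theatre cannot be recovered later.

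**What to change.** In sections 2.0 and 7.1, replace both start rules with one that applies to both arms: the moment the nail is fully seated, before any jig mounting or perfect-circle imaging for distal locking. End at the last shot confirming seating of the final distal interlock, and analyse that single interval per patient as the time outcome.

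A nail-seated start alone would miss mounting done earlier. So timestamp jig assembly and mounting, including attempts abandoned for freehand, and add any part done before seating to the jig arm's time. This is a recording rule and does not require surgeons to change the order of their work.

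Keep the first-shot-to-last-shot interval as a supporting result labelled as placement only, and report it beside skin-to-skin time.

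The cost is one or two extra timestamps per case and revised wording. The outcome becomes slightly broader and may be more variable, because it takes in any unrelated work between seating and distal locking, and the jig's saving may look smaller. Section 7.2 refers to patients already enrolled; where their mounting was not recorded, the new interval may be unavailable, and the report should say which clock was used for them.

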5.0 DATA COLLECTION AND MANAGEMENT

5.1 DATA PROCUREMENT

Data for this study will be procured from patient x-ray images retrieved from the picture archiving and communication software (PACS). Deidentified x-ray measurements will be stored in a HIPAA compliant Cedars Box folder.

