5.4 SOURCE DOCUMENTS

Source documents for this study will be radiographic images which we will take measurements from using PACS software and incorporated into a deidentified, secure database.

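### The operating surgeon, who knows the technique, self-records the powered time outcome from a wall clock with no independent check, and sections 2.0 and 7.1 start that clock at different events

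*Combined protocol and SAP*

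**What the plan says.** All references are to the combined protocol and SAP.

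- **Outcome.** Section 2.0 lists "Primary outcomes: radiation exposure, time, accuracy of placement (right angle to rod"), and treats each distal interlock as a separate outcome. Section 7.2 bases the sample size on interlock time alone.
- **Events in 2.0.** "The first fluoroscopy shot to localize the jig or obtain a perfect circle is considered start time". "The last shot to confirm complete seating of the screw will be considered end time".
- **Recorder in 2.0.** For each of these events, "The surgeon will note the hour, minute, and seconds of the time based on the wall clock in the operating room".
- **Start in 7.1.** The primary analysis covers the average time to place two interlocks, with "start time when nail is seated and surgeon states s/he is ready to proceed with distal interlocking screw placement". No separate end is given there.
- **Data sources.** Section 5.1 says "Data for this study will be procured from patient x-ray images retrieved from the picture archiving and communication software (PACS"). Section 5.4 says "Source documents for this study will be radiographic images which we will take measurements from using PACS software". Neither says that individual fluoroscopy shots are saved or carry a usable time stamp. Section 5.3 lists length of surgery but no interlock start or end time.
- **Checks.** Section 6.2 has a monitor confirm that appropriate data are recorded. No second recorder, independent timer or comparison source for the clock readings is described.

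**The concern.** The calendar sets the technique (section 4.0) and the surgeon carries it out, so the person timing the outcome cannot be blinded. That person is also operating while reading a clock to the second, at two moments for each screw. If the readings are off by a different amount under the two techniques, the difference enters the treatment comparison one for one, and more patients do not dilute it. It could create an apparent time saving or hide a real one. Unless the defining shots are kept, nobody could later tell which had happened.

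The conflict between 2.0 and 7.1 adds to this. Under 7.1 the start is a statement by the same surgeon, with no fluoroscopy shot to mark it. The interval between that statement and the first shot may also differ by technique, for example through jig set-up, so the two windows need not give the same treatment difference.

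**Working it through.** **Inputs from 7.1 and 7.2.** Means 616 s and 344 s; SD 192 s; two-sided t-test; 5% significance; 90% power; 75% participation; 9% outside the sub-study criteria.

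**1. The plan's own sample size.**
- Difference: 616 − 344 = 272 s, and 272/616 = 44%.
- n per technique = 2 × (1.960 + 1.282)² × 192² / 272² = 10.5, so 11, or 22 for the comparison. The exact t-test needs 11.5, so 12 per technique.
- 22/0.75 = 29.3, so 30. Two bone cohorts make 60. Then 60/0.91 = 65.9, so 66.

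The stated 30, 60 and 66 are reproduced if 30 is read as the size of each bone cohort. With an even split (an assumption) that is about 15 per technique within a bone, or 30 per technique with the bones pooled. Both are used below.

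**2. Error unrelated to technique.** Let each clock reading have an independent random error with SD e. The SD of the recorded time becomes √(192² + 2e²). The values of e are assumptions.

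| e (s) | SD of time (s) | n per technique |
|---|---|---|
| 5 | 192.1 | 11 |
| 15 | 193.2 | 11 |
| 30 | 196.6 | 11 |
| 60 | 209.9 | 13 |

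Only a large error (60 s at each end) moves the requirement, and then by two patients per technique.

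**3. Error that differs by technique.** Let b be the net difference in mean recording error, with no true difference in time. The t statistic is then noncentral, with noncentrality b / (192 × √(2/n)).
- n = 30: standard error 192 × √(2/30) = 49.6 s, 58 degrees of freedom, critical value 2.002.
- n = 15: standard error 192 × √(2/15) = 70.1 s, 28 degrees of freedom, critical value 2.048.

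The table gives the probability of two-sided rejection. The values of b are assumptions.

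| b (s) | b/272 | 30 per technique | 15 per technique |
|---|---|---|---|
| 0 | 0% | 5.0% | 5.0% |
| 15 | 6% | 6.0% | 5.5% |
| 30 | 11% | 9.1% | 7.0% |
| 60 | 22% | 22.2% | 13.1% |
| 90 | 33% | 43.1% | 23.6% |

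The inflation is larger at 30 than at 15 because a fixed bias stands out more against a smaller standard error.

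**4. The two windows side by side.**

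| | 2.0 | 7.1 |
|---|---|---|
| Start | First shot to localize the jig or find the circle | Nail seated and surgeon declares readiness |
| End | Last shot confirming seating | Not given |
| Unit | Each interlock | Two interlocks |
| Could an image time the start? | Yes, if saved and stamped | No |

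The 2.0 window could be checked against images; the 7.1 start could not.

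**The case against.** The strongest reply is that the events in 2.0 are concrete, the readings are to the second, and nothing in the documents suggests a systematic difference of 30 to 90 s between techniques. With a bias of 15 s the false-positive rate hardly moves. This stands: the table shows sensitivity and is not an estimate.

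Three further objections limit the point.

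- **A reader might infer from 5.1 and 5.4 that the shots already sit in PACS with time stamps.** The documents do not say so. Those sections describe x-ray images used for measurements. Whether intraoperative shots are saved and stamped must be confirmed with the site.
- **A reader might infer that wall-clock time is singled out as lacking a source document under 5.4.** Section 5.3 also lists radiation exposure and length of surgery, which are not measurements taken from a radiograph. Section 5.4 is incomplete in general, so it is weak evidence on this point.
- **A reader might infer that time stamps would remove observer bias.** They remove clock-reading error. The same team still judges which shot is the first or the last.

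None of this answers the central point: the recorder is unblinded, no check is described, and 2.0 and 7.1 disagree on the start.

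**Conclusion.** The concern holds as a weakness in how the powered outcome is measured, and it should be corrected. Unblinded self-recording without an independent check, and the conflict between the 2.0 and 7.1 windows, are both plain in the text.

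The size is conditional. At SD 192 s, a net differential error of 60 s, which is 22% of the planned effect, would raise the false-positive rate from 5% to about 22% with 30 per technique or 13% with 15. At 15 s the effect is negligible. These figures assume the planning SD, an even split between techniques and bias sizes that the documents do not supply. They also ignore any loss of data under the surgeon-experience rule in 7.1.

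Two stronger conclusions are not supported. The documents do not show that the recorded times are biased. Nor does this point make the sample size inadequate, since error unrelated to technique leaves it almost unchanged.

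**What to change.** 1. Reconcile 7.1 with 2.0 by using the shot-to-shot window in both, and state how the two-interlock time is formed from the separate interlock times.
2. In 2.0, require that the first and last defining shots for each interlock are saved: 2 shots × 2 interlocks = about four per case.
3. Ask the site whether the C-arm stores time-stamped shots. Where it does, take the primary time from the stamps and keep the wall-clock note as backup.
4. Flag every case that relies on the wall clock, including any patients already enrolled (7.2 refers to current enrolment). Report agreement between the two sources where both exist, and the time comparison with and without the flagged cases.
5. Add the interlock start and end times, with their source, to 5.3 and 5.4.

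If the site cannot supply time stamps, a second recorder in the room would give the independent check, at the price of extra staff.

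The cost is a few extra saved images per case, a short wording change and a mixed data source for earlier cases. Judgement about which shot is first or last remains.
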